Patients enrolled in the operative treatment group will undergo surgical intervention for their pelvic fracture. The surgeon will decide the best surgical technique as per standard of care for the patient's injury. The patient will mobilize as per the surgeon's instructions and x-rays will be taken at follow-up clinic appointments to determine if the injury is healing properly. If additional surgery is required or other complications arise, this will be recorded within the study follow-up forms.

CLINICAL EVALUATION

A summary of the clinical evaluations is outlined below and can also be found in Appendix B.

Medical Record Review

During the index hospitalization, information about the participant (medical history, height and weight, etc.) and the participant's injuries and hospital stay will be collected, including mechanism, presence of and severity of other orthopaedic and non-orthopaedic injuries, procedures done in the hospital, overall (and ICU) length of stay, time to mobilization (bed to chair) in physical therapy, pain medication administration, and discharge disposition.

Assessment of Study Injuries

The extent and severity of the pelvic injury will be prospectively assessed by the treating surgeon after initial x-rays are taken. The following injury characteristics will be collected:

- Lateral compression type classification of the pelvic fracture
- Skin defect associated with the pelvic injury
- Muscle and tendon injury associated with the pelvic injury
- Deep vein injury associated with the pelvic injury
- Nerve injury associated with the pelvic injury

Assessment of Study Injury Treatment

For participants undergoing operative treatment, the following information will be obtained:

- Type of fracture stabilization
- Type and timing of fixation revisions
- Limb Complications (type, severity, treatment)

Assessments at 2 weeks, 6 weeks, 3 months, and 1 year post injury

- Complications since last follow-up (type, severity, treatment)
- Assessment of fracture healing
- Weight bearing status and ambulation
- Use of ambulatory devices
- Pain assessment
- Narcotic use assessment

X-rays

AP and lateral x-rays at admission, post-operative treatment (when applicable), and at the 2 week, 6 week, 3 month and 1 year follow-ups will be obtained. These x-rays are obtained per standard of care.

PARTICIPANT INTERVIEWS

A summary of the participant interviews performed are outlined below and can also be found in Appendix D.

Baseline Hospital Interview

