Our primary hypothesis is that the operative treatment group will have lower VAS pain scores compared to the non-operative treatment group both during their hospital stay and in the short-term outpatient follow-up.

Based on the results of a pilot study, we expect pain scores in the non-operative group to have a mean of 5.7 and a standard deviation of 2.3. Assuming a 20% reduction in pain scores, 130 patients (65 per arm) are required to have an 80% chance of detecting, as significant at the 5% level, a decrease in the primary outcome measure from 5.7 in the control group to 4.56 in the experimental group. This is our primary outcome and the study will be powered for this variable.

Primary data analysis will involve direct comparison of the change in value of the reported pain scores at the time points listed below. We will be powered to detect a 20% reduction in pain. Secondary analysis will compare the value of narcotics administered at the distinct time periods. Tertiary analysis will be comparing the time (in days) to mobilization with physical therapy. The previous retrospective pilot study incorporated a propensity factor, generated from well documented sources of pain. As this is a prospectively randomized trial, we do not anticipate needing to accommodate for matching.

RANDOMIZATION

Eligible patients will be randomized in equal proportions to one of the two treatment groups: 1) operative treatment of the lateral compression type fracture, 2) non-operative treatment of the lateral compression type fracture. Allocation will be concealed using a centralized 24-hour computerized randomization system, www.randomize.net, that will allow Internet based allocation. The treatment allocation will be stratified on the following prognostic factors to ensure balance between the intervention groups: 1) patient intubation status at time of enrollment, 2) patient prescription pain medication usage during the month prior to injury.

DATA MANAGEMENT

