**Pelvis RCT: Impact of Surgery on Pain in Lateral Compression Type Pelvic Fractures**

**NCT: 02625766**

**December 28, 2020**

### Statistical Analysis

[figure not shown]
The primary analyses were based on the intent-to-treat principle. The primary analysis for pain and secondary analysis for functional outcome estimated the difference in the average treatment effect based on a longitudinal assessment within the initial 12-weeks after the fracture. This approach uses each patient's multiple outcome assessments to compare the average pain and function experienced over the 12-week period between the treatment groups. For these analyses, we used a Bayesian hierarchical model that applied a prior probability of no treatment difference based on the conflicting evidence in the prior literature [3-6]. This is akin to an initial assumption that there is "no difference" in pain or functional outcome between the treatment groups. In addition to estimating the average treatment effect, we calculated the posterior probability (meaning conditioning the prior distribution on the data at hand) of treatment benefit with operative treatment under various minimally clinical important difference (MCID) thresholds. The models included a dummy variable for each patient as a random intercept, an autoregressive correlation structure, and adjusted for whether the treatment was randomly assigned, the patient's pre-injury narcotic use, and a time-varying covariate that measured narcotic use at each time point. Multivariable linear regression was used to analyze the treatment effect on hospital length of stay and time to mobilization. Outcome data were missing in 16% of the sample at 2-weeks, and 14% of the sample at 6-weeks and 12-weeks, and was therefore imputed using multiple imputation for the final models [16]. To assess possible effect measure modification based on the initial degree of displacement, we stratified the sample to create two subgroups, patients with  $\geq 5$ mm of displacement and patients with  $< 5$ mm of displacement. We then calculated the average effect of operative treatment on pain in each of the subgroups. In addition, we compared the average treatment effect of operative fixation on pain with posterior-only fixation compared to operative fixation with anterior and posterior fixation. Additional sensitivity analyses recalculated the pain and function outcomes to separately compare the treatment effects between patients enrolled in the randomized cohort and the observational cohort. The analyses were performed using R Version 3.6.1 (Vienna, Austria) with the packages *lme4*, *rstan*, *brms*, and *mice*.

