**Posterior probability of reduced pain, stratified by initial posterior pelvic ring fracture displacement:** The posterior probability of surgical fixation achieving a clinically significant reduction in mean BPI pain scores stratified by fracture displacement (<5mm versus  $\geq$ 5mm). Several possible clinically significant pain reduction thresholds are presented.

	Displacement $\geq$ 5mm	Displacement < 5mm	Difference in Probability
Mean Difference in Pain	2.2 (95% CrI: 0.9 - 3.5)	0.9 (95% CrI: 0.1 - 1.8)	
> 0	> 99%	98%	2%
> 0.5	99%	82%	17%
> 1.0	97%	41%	56%
> 1.5	88%	8%	80%
> 2.0	65%	1%	64%

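### The SAP labels its posterior-only versus anterior-plus-posterior comparison a treatment effect, but surgeons choose the technique and no injury-severity adjustment is described

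*SAP*

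**What the plan says.** The SAP (Statistical Analysis) adds a technique comparison to its subgroup work: "we compared the average treatment effect of operative fixation on pain with posterior-only fixation compared to operative fixation with anterior and posterior fixation". It gives no comparator, group sizes, covariates or result for this comparison.

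The covariates given for the pain and function models are these: the models "adjusted for whether the treatment was randomly assigned, the patient's pre-injury narcotic use, and a time-varying covariate that measured narcotic use at each time point". Displacement enters only through a separate operative versus non-operative analysis: "To assess possible effect measure modification based on the initial degree of displacement, we stratified the sample to create two subgroups", cut at 5 mm. Lateral compression (LC) class does not appear in the SAP's adjustment.

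On allocation, the protocol (Randomization) says "Eligible patients will be randomized in equal proportions to one of the two treatment groups", meaning operative or non-operative. The stratification factors are intubation status and recent prescription pain medication. On technique, the protocol (Study Treatments, Operative Treatment Group) says "The surgeon will decide the best surgical technique as per standard of care for the patient's injury". LC types 1, 2 and 3 are all eligible (Study Population). LC class and type of stabilization are both recorded (Clinical Evaluation).

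**The concern.** Randomization protects the comparison of surgery with no surgery. It does not protect a comparison between two ways of operating when the surgeon picks the technique in view of the injury. Each technique group is then a selected part of the operative patients, and a difference in pain between the groups mixes technique with injury. In the pooled observational cohort, surgery itself was not randomly assigned either.

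None of the listed covariates describes the injury, yet the SAP itself treats displacement as a possible effect modifier and tabulates different benefits on either side of 5 mm. It also adjusts for willingness to be randomized while saying there was no evidence that this affected treatment. By that standard, injury severity has at least as good a claim to adjustment in the technique contrast.

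At stake is the interpretation of a secondary result. A technique could look better or worse because of the injuries it was used for, and calling the result an average treatment effect invites a causal reading that the design does not support.

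**Working it through.** **1. Inputs.** From the SAP's displacement table: mean reduction in pain with surgery 2.2 (95% credible interval 0.9 to 3.5) at 5 mm or more, and 0.9 (0.1 to 1.8) below 5 mm. Not given anywhere: the share of displaced fractures in each technique group, and the effect of displacement on pain without surgery.

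**2. Reproducing the table.** Treat each posterior as normal, with SD = interval width / 3.92.
- 5 mm or more: (3.5 - 0.9) / 3.92 = 0.663
- Below 5 mm: (1.8 - 0.1) / 3.92 = 0.434

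The probability of exceeding a threshold t is Phi((mean - t) / SD).

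| Threshold | >= 5 mm, printed | >= 5 mm, recomputed | < 5 mm, printed | < 5 mm, recomputed |
|---|---|---|---|---|
| 0 | > 99% | > 99% | 98% | 98% |
| 0.5 | 99% | 99% | 82% | 82% |
| 1.0 | 97% | 96% | 41% | 41% |
| 1.5 | 88% | 85% | 8% | 8% |
| 2.0 | 65% | 62% | 1% | 1% |

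The gaps in the >= 5 mm column close within rounding of the printed inputs: a mean of 2.249 with SD 0.638 gives 88.0% and 65.2% in the last two rows. The table can be used as printed.

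**3. How strongly the table points to displacement.** Difference = 2.2 - 0.9 = 1.3. Treating the subgroups as independent, SE = sqrt(0.663^2 + 0.434^2) = 0.79. The approximate 95% interval is 1.3 +/- 1.96 x 0.792, or -0.25 to 2.85, and the probability that the difference exceeds zero is about 95%. This is suggestive, not established; the SAP reports no interaction estimate.

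**4. What an unadjusted technique contrast would show if technique did nothing.** Let mean pain without surgery be m below 5 mm and m + d at 5 mm or more. Mean pain with surgery is then m - 0.9 and m + d - 2.2, so operated patients differ between strata by d - 1.3. If the two technique groups have displaced shares p1 and p2,

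contrast (group 1 minus group 2) = (p1 - p2) x (d - 1.3).

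Comparing each technique with the same pooled non-operative group gives the same size, because the non-operative mean cancels.

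**5. Results under assumed values.** Points of pain; a negative value makes the technique used more often in displaced fractures look better.

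| Share difference (assumed) | d = 0 | d = 0.65 | d = 1.3 | d = 2.6 |
|---|---|---|---|---|
| 20 points | -0.26 | -0.13 | 0 | +0.26 |
| 50 points | -0.65 | -0.33 | 0 | +0.65 |

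The 1.3 is itself uncertain. At d = 0 and a 50-point share difference, its interval limits give -0.5 x 2.85 = -1.43 and -0.5 x (-0.25) = +0.13.

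**6. Why adjustment works without knowing d.** Among operative patients, a displacement term absorbs d - 1.3 as one coefficient. Within each stratum the contrast is then zero when technique has no effect, on the assumption that any technique effect is the same in both strata.

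**The case against.** The strongest reply is that the link from injury to technique is assumed. The table stratifies by posterior ring displacement, both technique groups have posterior fixation, and they differ in the added anterior fixation. No passage says that posterior displacement or LC class decides that addition. This stands: the documents establish that technique follows the injury, not which feature of it, and the shares used above are illustrations.

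A second reply is that the SAP lists no covariates for this particular contrast. That also stands. The finding is that adjustment is not described, not that none was done.

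A reader might go further and multiply 1.3 by a share difference, take 0.26 to 0.65 points as the bias, set it against the 1.14-point design difference (20% of 5.7), and suppose that any direct effect of displacement on pain only enlarges it. The documents do not support this. Those figures require d = 0. If displaced fractures hurt more without surgery, d first offsets the 1.3 and can cancel or reverse it. And 1.14 is the planned difference between operative and non-operative care, not a target for this contrast.

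Finally, this is one additional analysis with no result shown in the SAP, and the technique groups may be too small for rich adjustment: the protocol plans 65 patients per arm, and the SAP gives no split by technique. This limits the remedy but does not make the label accurate.

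**Conclusion.** The concern holds in a limited form. Technique is not randomized, the surgeon chooses it for the injury, and the listed covariates contain no injury-severity variable. As described, the contrast is open to confounding by indication and should not be called an average treatment effect.

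Neither the size nor the sign of any bias can be determined. It depends on the displacement mix by technique and on d, and the documents report neither. The illustrated range of -0.65 to +0.65 points rests on an assumed 50-point share difference, d between 0 and 2.6, and a 1.3-point difference whose approximate interval includes zero. It would be wrong to infer that a spurious advantage for either technique has been shown, or that the primary operative versus non-operative comparison is affected.

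**What to change.** Estimate the technique contrast among operative patients only. Adjust for the displacement measure the SAP already uses (5 mm or more versus less, or the continuous value if it was recorded) and for LC class, collapsing classes if cells are sparse. Tabulate both variables by technique so that readers can see how far the groups differ. State the covariates and group sizes for this analysis, and report the result as a non-randomized exploratory association instead of an average treatment effect.

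No new data are needed: displacement was used in the SAP, and the protocol provides for recording LC class and type of stabilization. The cost is a wider interval and, in small technique groups, adjustment that may be incomplete. If adjustment proves unworkable, the table and the relabelling can still be done.

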
We took two critical steps to understand the potential for biased treatment estimates from pooling the results from the randomized and non-randomized participants. First, we performed sensitivity analyses to separately examine the results for the randomized and non-randomized cohorts. These analyses suggested similar (or even larger) estimated treatment benefits from surgery within the RCT data. Second, we included willingness to be randomized as a potentially confounding variable in our final analysis models, despite there being no evidence that it affected treatment.

[figure not shown]
The ability to assess the probability of different magnitudes of treatment benefit is a unique characteristic of Bayesian data analysis, and is not possible with traditional non-Bayesian statistical hypothesis testing. Despite this inherent difference in statistical principles, it should be noted that the average treatment benefits reported from our Bayesian analysis are nearly identical to the results obtained using traditional multilevel linear regression models (results not reported).

Additional results from the described analyses, that were not included in the main article, are provided below.

[figure not shown]
**Posterior probability of reduced pain.** Posterior probability of reduced pain with operative treatment within 12 weeks of injury.

[figure not shown]
**Mean pain stratified between randomized and nonrandomized patients.** The mean Brief Pain Inventory scores and 95% credible intervals within the initial 12-weeks of injury for minimally displaced complete lateral compression pelvis fracture patients. The patients are stratified based on their study type (randomized trial versus observation) and treatment type (operative versus nonoperative treatment). The pain scores are adjusted for the study type, prior narcotic use, and narcotic use at each time point.

**Posterior probability of improved function.** Posterior probability of improved function, measured with the Majeed score, with operative treatment within 12 weeks of injury.

**Mean function stratified between randomized and nonrandomized patients.** The mean Majeed scores and 95% credible intervals within the initial 12-weeks of injury for minimally displaced complete lateral compression pelvis fracture patients. The patients are stratified based on their study type (randomized trial versus observation) and treatment type (operative versus nonoperative treatment).

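### The primary pain analysis, labelled intent-to-treat, pools randomised patients with patients who declined randomisation; pre-injury narcotic use is the only baseline patient factor it adjusts for

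*SAP*

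**What the plan says.** Under Description of the Study Design and Informed Consent, the protocol offers an observational arm to patients who decline randomisation, and only after they decline. Under Data Analysis it sees no need for matching, because the trial is randomised.

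The SAP (Statistical Analysis) opens with "The primary analyses were based on the intent-to-treat principle". It then describes a Bayesian hierarchical model for average pain over 12 weeks, with a patient random intercept and autoregressive correlation. The model is "adjusted for whether the treatment was randomly assigned", for pre-injury narcotic use, and for "a time-varying covariate that measured narcotic use at each time point". The first of these covariates makes sense only if both cohorts are in the model, and a later paragraph confirms the pooling when it takes up "the potential for biased treatment estimates from pooling the results from the randomized and non-randomized participants".

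The SAP gives two safeguards. Sensitivity analyses "separately compare the treatment effects between patients enrolled in the randomized cohort and the observational cohort", with the reported result: "These analyses suggested similar (or even larger) estimated treatment benefits from surgery within the RCT data". Willingness to be randomised was also put in the final models, "despite there being no evidence that it affected treatment".

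**The concern.** The protocol summary sets out to estimate a causal effect of operative against non-operative treatment. In the randomised cohort, allocation supports that. In the observational cohort, treatment was not allocated at random, and a factor that influences both the choice of surgery and later pain would confound the comparison. A pooled estimate mixes the two contrasts.

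The SAP's second safeguard does not reach this problem. Willingness to be randomised describes which cohort a patient is in. The open question is what separates operated from non-operated patients among those who declined. The protocol's reason for not matching does not apply to them either.

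At stake is how much of the headline estimate rests on randomisation, and how far agreement between the cohorts can make up for the part that does not.

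**Working it through.** **1. What each model term can do inside the observational cohort**

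| Term | Inside the observational cohort |
|---|---|
| Randomly assigned, yes/no | Constant; absorbs a mean difference between cohorts only |
| Pre-injury narcotic use | Baseline; can adjust for treatment choice related to it |
| Narcotic use at each time point | Measured after treatment, and a secondary outcome in the protocol; not a baseline confounder |
| Random intercept, autoregressive structure | Model within-patient correlation, not treatment choice |

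Fracture class, age and severity of other injuries are collected (protocol, Clinical Evaluation and Participant Interviews). Displacement is used in the SAP for subgroups. None is a listed covariate.

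**2. The planned effect**

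Protocol, Data Analysis: mean 5.7 against 4.56, SD 2.3, 80% power, 5% level. The difference is 5.7 − 4.56 = 1.14. A two-sided two-sample t-test needs 64.87, so 65 per arm, as stated.

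**3. Precision implied by the SAP's displacement table**

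SE = interval width / 3.92.
- ≥5 mm: (3.5 − 0.9)/3.92 = 0.663
- <5 mm: (1.8 − 0.1)/3.92 = 0.434

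Normal check against the table's posterior probabilities:
- ≥5 mm, above 0.5/1.0/1.5/2.0: 99.5/96.5/85.4/61.8% (table 99/97/88/65)
- <5 mm, above 0/0.5/1.0/1.5/2.0: 98.1/82.2/40.9/8.3/0.6% (table 98/82/41/8/1)

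Agreement is within about 3 percentage points.

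Combined SE = 1/√(1/0.663² + 1/0.434²) = 0.363, half-width 1.96 × 0.363 = 0.71. The inverse-variance mean is 1.29, interval 0.58 to 2.00.

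**4. Difference between cohort effects, and the randomised cohort alone**

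Assumptions: the two strata make up the analysed sample, information per patient is equal, and the observational share f is assumed because the readable documents give no cohort sizes.
- SE of the cohort difference = 0.363/√(f(1−f))
- SE of the randomised-only estimate = 0.363/√(1−f)

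| f | Half-width, cohort difference | Difference detectable with 80% power (2.80 × SE) | Half-width, randomised only | Randomised-only interval if its effect is 1.29 |
|---|---|---|---|---|
| 0.25 | 1.64 | 2.35 | 0.82 | 0.47 to 2.11 |
| 0.50 | 1.42 | 2.03 | 1.01 | 0.28 to 2.30 |
| 0.67 | 1.51 | 2.16 | 1.24 | 0.05 to 2.53 |

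f(1−f) is largest at f = 0.5, so 1.42 is the minimum at any split. The table's bounds are rounded to 0.1, so each width could be off by up to 0.1. With widths of 2.5 and 1.6 the minimum is 1.35; with 2.7 and 1.8 it is 1.50.

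**5. Mechanism only**

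A large-sample linear regression was simulated with assumed inputs: no true effect, half the patients observational, one unlisted severity factor worth 1 pain point per SD, and log-odds of surgery per SD of −0.5, 0.5 or 1 in the observational cohort. The pooled bias was −0.24 to +0.43 points. It was the same with and without the cohort indicator and pre-injury narcotic use. Randomised-only estimates stayed within 0.02 of zero. The sign follows the assumed direction of treatment choice, so this says nothing about the size or direction of bias in this trial.

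**The case against.** The SAP is open about the pooling. It names the risk, analyses the cohorts separately and reports benefit in the randomised data at least as large. Inclusion criterion 6 requires that the patient be suitable for either treatment, which narrows confounding by indication. Benefit appears in both displacement strata (2.2 and 0.9), so displacement across the 5 mm cut cannot alone explain the pooled effect. All of this stands.

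The calculations measure precision at assumed splits, not bias. Cohort-specific means with credible intervals are in figures not available here. The 1.14 is a planned two-week effect, whereas the displacement table comes from a 12-week average analysis, so that comparison gives scale only. This also stands.

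A reader might infer that intent-to-treat has no meaning for patients who were never allocated. That goes too far. They could be analysed by the treatment first chosen, and the protocol's Study Treatments section speaks of patients enrolled in each group with crossover recorded. The readable text does not state the rule, but the consent attachment or the enrolment figure may.

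Making the randomised cohort the headline now would promote, with results known, the subset already reported as similar or more favourable. It could also cost power. On the planning inputs, power would be 0.68, 0.50 or 0.28 if 75%, 50% or 25% of 130 patients were randomised (assumed shares). The recommendation therefore does not depend on that switch.

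**Conclusion.** The concern holds as a limit on what the headline estimate can support. Part of that estimate does not rest on randomisation, and within that part the model adjusts for one baseline patient factor.

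A reader might infer that pooling inflated or created the benefit. The documents do not support this. The SAP's separate-cohort statement points the other way, and at each assumed split the randomised-only interval would still exclude zero if its effect were 1.29.

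The reassurance from similar cohort results is weak: the cohort difference would carry a half-width of at least about 1.42 points, beside a planned effect of 1.14. This rests on the strata making up the sample, on equal information per patient, and on the normal approximation. The unseen cohort-specific intervals could refine it.

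A reader might also infer that initial pain can never be adjusted for. The data collection schedule (protocol, Appendix B) shows only that no BPI is planned before 96 hours, so a pre-treatment value is not assured.

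This should be fixed. Confidence is medium.

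**What to change.** 1. Add baseline factors already collected or used (fracture class, displacement, age, associated injuries) to the pooled model, by covariate adjustment or propensity weighting. Pre-injury narcotic use is already there.
2. Report the randomised-cohort estimate by assigned arm, with its 95% credible interval, beside the pooled estimate. Confirm that the existing separate-cohort model used assigned arm, or refit it. Crossover is allowed (protocol, Non-operative Treatment Group), and the SAP's cohort figure captions describe the groups by "randomized trial versus observation) and treatment type (operative versus nonoperative treatment", which leaves this open.
3. Report the difference between the cohort effects with its 95% credible interval.
4. Reserve intent-to-treat for the randomised comparison, or state that observational patients were classified by initially chosen treatment, if that is what was done.

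If the randomised comparison is also made the headline result, declare that this was done with results known and after its estimate had been reported as similar or larger.

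Cost: one adjusted or weighted pooled model, one model confirmed or refitted, and some rewording; no new data. The randomised-only interval will be wider, about ±0.82 to ±1.24 against ±0.71 pooled, at assumed randomised shares of 75% to 33%.
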